18.4.1. EXPLORATORY EFFICACY VARIABLES & DERIVATIONS

- Mean change from baseline in the Patient Global Impression of Severity (PGI-S) at Month 3
- The overall mean change from baseline in the number of monthly moderate to severe

Document: **CCI**

Author: **PPD**

Version Number:

3.0

Version Date:

19May2023

CCI

- headache days across the 3-month double-blind treatment period
- Mean change from baseline in the Monthly Total Pain Burden across the 3-month double-blind treatment period

Additional exploratory endpoints to assess onset of action:

- Mean change from baseline in the number of weekly migraine headache days in the months that galcanezumab was superior to rimegepant
- Percentage of participants with $\geq 50\%$ reduction from baseline in monthly migraine headache days at Month 3, Month 2, and Month 1
- Percentage of participants with $\geq 50\%$ reduction in Weekly migraine headache days at weeks 4, 3, 2, 1, in the months that galcanezumab was superior to rimegepant

Additional exploratory endpoint to assess sustained response:

The initial month at which galcanezumab was superior to rimegepant in the proportion of patients meeting at least a 50% reduction in monthly migraine headache days that is sustained at all subsequent months through Month 3

Other exploratory endpoints of interest:

- The overall mean change from baseline in the number of monthly days with acute headache medication use during the 3-month double-blind treatment phase (this is based on any day). Medication use will be based on response to question 12 in the diary.
- The overall mean change from baseline in the number of monthly moderate to severe migraine headache days across the 3-month double-blind treatment period (– Only includes Migraine Headache day)
- Percentage of participants with $\geq 50\%$ reduction from baseline in moderate to severe monthly migraine headache days across the 3-month double-blind treatment period

18.4.2. MISSING DATA METHODS FOR EXPLORATORY EFFICACY VARIABLE(S)

Two statistical approaches to handling missing data will be used as appropriate: repeated

Document: **CCI**

Author: **PPD**

Version Number:

3.0

Version Date:

19May2023

CCI

measures analyses and ANCOVA model using change from baseline Month 3 of treatment period.

For the repeated measures analyses, the model parameters are simultaneously estimated using restricted likelihood estimation incorporating all of the observed data. Estimates have been shown to be unbiased when the missing data are missing at random.

18.4.3. ANALYSIS OF EXPLORATORY EFFICACY VARIABLES

18.4.3.1. Analysis of Mean Change from Baseline in the Patient Global Impression of Severity (PGI-S) at Month 3

For this continuous efficacy variable without repeated measures, an ANCOVA model with contains the main effects of treatment, and the continuous fixed covariate of baseline. Type III sum-of-squares for the LSMeans will be used for the statistical comparisons.

18.4.3.2. Analysis of the Overall Mean Change from Baseline in the Number of Monthly Moderate to Severe Headache Days Across the 3-month Double-blind Treatment Period

This endpoint with repeated measures will be analyzed using MMRM methods. The MMRM will include the fixed categorical effects of treatment, month, and treatment-by-month interaction, as well as the continuous fixed covariates of baseline and baseline-by-month interaction. Wherever possible an unstructured covariance matrix will be used to model the correlation structure among repeated measures.

18.4.3.3. Analysis of Mean Change from Baseline in the Monthly Total Pain Burden Across the 3-month Double-blind Treatment Period

This endpoint with repeated measures will be analyzed using MMRM methods. The MMRM will include the fixed categorical effects of treatment, month, and treatment-by-month interaction, as well as the continuous fixed covariates of baseline and baseline-by-month interaction. Wherever possible an unstructured covariance matrix will be used to model the correlation structure among repeated measures.

18.4.3.4. Analysis of Additional Exploratory Endpoints

The additional change from baseline exploratory endpoints with repeated measures will be analyzed using MMRM methods. The MMRM will include the fixed categorical effects of treatment, month, and treatment-by-month interaction, as well as the continuous fixed covariates

Document: **CCI**

Author: **PPD**

Version Number:

3.0

Version Date:

19May2023

CCI

of baseline and baseline-by-month interaction. Wherever possible an unstructured covariance matrix will be used to model the correlation structure among repeated measures.

The additional binary exploratory variables with repeated measures will be analyzed using a GLIMMIX as pseudo- likelihood-based mixed effects repeated measures analysis. The GLIMMIX procedure will include the fixed, categorical effects of treatment, month, and treatment-by-month interaction, as well as the continuous, fixed covariate of baseline value.

19. QUALITY OF LIFE ANALYSIS

Quality of Life (QoL) will be analyzed under efficacy analyses.

20. SAFETY OUTCOMES

Safety endpoints consist of incidences of treatment emergent adverse events (TEAEs), serious adverse events (SAEs) and adverse events (AEs) in general and leading to discontinuation, vital signs (blood pressure, pulse, and body temperature), weight and laboratory measures (chemistry, hematology, and urinalysis). All outputs for safety outcomes will be based on the Safety Analysis Set.

For categorical safety variables (such as AEs and other categorical changes of interest), comparisons between treatment groups will be performed using Fisher's exact test.

20.1. ADVERSE EVENTS

Adverse Events (AEs) will be coded using MedDRA central coding dictionary, Version 24.1 or higher. Treatment-emergent adverse events are defined as the reported AEs that first occurred or worsened during the post-baseline phase compared with baseline phase. Adverse events (AE) that occurred on the visit date of Visit 3 will be determined to be pre-dose or after dose based on AE start time and the injection time: pre-dose if AE start time is before the injection time; post dose if AE start time is after the injection time.

For each TEAE, the severity level of the event (mild, moderate, or severe) will be determined by participant or physician opinion. The MedDRA Lowest Level Term (LLT) will be used in the treatment emergent computation. For each LLT, the maximum severity at baseline will be used

Document: CCI

Author: PPD

Version Number:

3.0

Version Date:

19May2023

CCI

as the baseline severity. If the maximum severity during post-baseline is greater than the maximum baseline severity, the event is considered to be treatment emergent for post-baseline period. For each participant and TEAE, the maximum severity for the MedDRA level being displayed (PT) is the maximum post-baseline severity observed from all associated LLTs mapping to that MedDRA level. Summary tables will present events by PT by decreasing frequency of PT or by SOC/PT and by decreasing frequency of PT within SOC.

See APPENDIX 2 for handling of partial dates for AEs. In the case where it is not possible to define an AE as treatment emergent or not, the AE will be classified by the worst case; i.e. treatment emergent.

An overall summary of number of participants within each of the categories described in the sub-section below, will be provided as specified in the templates. Listings will include TEAEs and Non-TEAEs.

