Visit 1 procedures may be conducted over more than 1 day as long as all activities are completed within the allowable visit tolerance.								
Visit Number	1	2	3	4 a	5 a	6		
Month relative to randomization (V3)	*	**		1	2	3		
*Screening lasts from 3 to 30 days.
 
** Eligibility is determined between a minimum of 30 days and a maximum of 40 days. Investigators have up to 5 additional days, if needed, to schedule participant's Visit 3 appointment.
 
For scheduling purposes, a month is 30 days.

Interval allowance (days)			-	±2	±2	±2		
Telephone Visit				X	X			See footnote a.
Participant training video (self-injection of study intervention)		X						
MSQ v2.1			X			X	X	Participant-rated assessments completed onsite should be completed prior to administration of study intervention and clinical examination.
MIDAS			X			X	X	
PGI-S			X			X	X	
Randomization and Dosing								
Randomization			X					
Study intervention administration at site (SC and ODT)			X					Study intervention will be administered by unblinded study personnel onsite at V3 (both SC and ODT) after all other visit procedures are completed.
Dispense study intervention and ancillary supplies			X					Study intervention is dispensed by unblinded study personnel in ancillary containers.
Administration of ODT study intervention at home				X				Participants will self-administer their ODT every other day at home.
Administration of SC study intervention at home				X	X			Participants to self-administer the SC study intervention at home prior to the telephone visit with the study site.
Return unused study intervention and ancillary supplies						X	X	Return any unused study intervention in the ancillary containers to unblinded site personnel.

Abbreviations: AE = adverse event; ECG = electrocardiogram; ePRO = electronic patient-reported outcomes; ET = early termination; FSH = follicle stimulating hormone; ICF = informed consent form; MIDAS = Migraine Disability Assessment; MSQ v2.1 = Migraine-Specific Quality of Life Questionnaire version 2.1; ODT = orally disintegrating tablet; PGI-S =Patient Global Impression of Severity; SC = subcutaneous; SP = study period; UDS = urine drug screen; V = visit; WOCBP = woman of childbearing potential.

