5.2. SAFETY ANALYSIS SET (SAF)

The safety analysis set (SAF) will contain all participants who are exposed to study intervention (either injection or ODT). Participants will be analyzed according to the treatment they actually received.

If there is any doubt whether a participant was treated or not, it will be assumed that the

Document: CCI

Author: PPD

Version Number:

3.0

Version Date:

19May2023

CCI

participant has been treated for the purposes of analysis.

When change from baseline is assessed, the participant will be included in the analysis only if the participant has a baseline and a postbaseline measurement.

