6. GENERAL CONSIDERATIONS

6.1. REFERENCE START DATE AND STUDY DAY

Study Day will be calculated from the reference start date and will be used to show start/stop day of assessments and events. It will appear in every listing where an assessment date or event date appears. Reference start date is defined as the day of the first dose of study intervention.

Study day will be computed as follows:

Study Day = (Date of event – Date of first dose of study treatment) + 1 if the date of the event is on or after the date of the first dose of study treatment;

Study Day = (Date of event – Date of first dose of study treatment) if the date of the event is prior to the date of the first dose of study treatment;

where the event can be an adverse event, medical history event, start/end of concomitant medication, laboratory assessment, etc.

In the situation where the event date is partial or missing, the date will appear partial or missing in the listings.

For participants who are randomized but do not receive study treatment, study day will be calculated using the date of randomization as the reference start date.

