6.2. BASELINE AND POST-BASELINE

Unless otherwise specified, baseline is defined as the last non-missing measurement taken prior to reference start date (including unscheduled assessments). If the time of the measurement is collected, both the date and time will be used to determine the baseline. For example, if assessments collected at Visit 1 to Visit 3 (prior to dosing at Visit 3, and this can be confirmed

Document: CCI

Author: PPD

Version Number:

3.0

Version Date:

19May2023

CCI

by time of the assessment and dosing time), the last non-missing measurement at Visit 3 prior to the first dosing will be counted as baseline. In the case where the last non-missing measurement and the reference start date coincide and the time is not collected, that measurement will be considered pre-baseline if the assessment is planned per protocol to take place prior to the first dose of study medication.

Vital Parameters (Pulse, SBP, and DBP) as these are captured in triplicates. Baseline and post-baseline will be the mean of the triplicate value. If only one value available then that value is used, if 2 values are available then the 2 values are averaged and used for the value at that visit.

Adverse Events (AEs) and medications commencing on the reference start date will be considered post-baseline unless otherwise indicated based on available start date/time combination or collected eCRF information that identifies the individual event/medication as starting prior to first study medication administration.

For treatment emergent abnormal laboratory or vital signs, the baseline criterion considers all predose records, instead of the last record only. That is

- A treatment-emergent abnormal result is defined as a change from normal at all predose/baseline visits to abnormal at any time during the treatment period. Patients with all normal values at predose/baseline will be included in the analysis of treatment-emergent abnormal laboratory values
- A treatment-emergent high result is defined as a change from a value less than or equal to the high limit at all predose/baseline visits to a value greater than the high limit at any time during the treatment period. Patients with all normal or low values at predose/baseline (no high values) will be included in the analysis of treatment-emergent high laboratory values.

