APPENDIX 2. PARTIAL DATE CONVENTIONS

Imputed dates will NOT be presented in the listings.

ALGORITHM FOR TREATMENT EMERGENCE OF ADVERSE EVENTS:

AE START DATE	AE STOP DATE	ACTION
Known	Known/Partial/ Missing	If start date < study med start date, then not TEAE If start date >= study med start date, then TEAE
Partial, but known components show that it cannot be on or after study med start date	Known/Partial/ Missing	Not TEAE
Partial, could be on or after study med start date OR Missing	Known	If stop date < study med start date, then not TEAE If stop date >= study med start date, then TEAE
	Partial	Impute stop date as latest possible date (i.e. last day of month if day unknown or 31st December if day and month are unknown), then: If stop date < study med start date, then not TEAE If stop date >= study med start date, then TEAE
	Missing	Assumed TEAE

Document: **CCI**

Author: **PPD**

Version Number:

3.0

Version Date:

19May2023

CCI

AE START DATE	AE STOP DATE	ACTION

ALGORITHM FOR PRIOR / CONCOMITANT MEDICATIONS:

CM START DATE	CM STOP DATE	ACTION
Known	Known	If stop date < study med start date, assign as prior If stop date >= study med start date and start date <= end of double-blind treatment period, assign as concomitant
	Partial	Impute stop date as latest possible date (i.e. last day of month if day unknown or 31st December if day and month are unknown), then: If stop date < study med start date, assign as prior If stop date >= study med start date and start date <= end of double-blind treatment period, assign as concomitant
	Missing	If stop date is missing could never be assumed a prior medication If start date <= end of double-blind treatment period, assign as concomitant
Partial	Known	Impute start date as earliest possible date (i.e. first day of month if day unknown or 1st January if day and month are unknown), then: If stop date < study med start date, assign as prior If stop date >= study med start date and start date <= end of double-blind treatment period, assign as concomitant

Document: **CCI**Author: **PPD**

Version Number:

3.0

Version Date:

19May2023

CM START DATE	CM STOP DATE	ACTION

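### On the first dosing day, SAP 20.1 times adverse events against the injection alone, which conflicts with SAP 6.2 when the tablet comes first; Appendix 2 conflicts with both for events before any dose

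*SAP*

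**What the plan says.** Four places in the SAP bear on whether an event on the first dosing day is treatment-emergent.

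- **SAP 20.1.** A Visit 3 event is classed by one clock only: "pre-dose if AE start time is before the injection time; post dose if AE start time is after the injection time". The tablet time is not mentioned. The section adds that an event whose status cannot be determined is taken as treatment-emergent (the worst-case default).
- **SAP 6.2.** "Adverse Events (AEs) and medications commencing on the reference start date will be considered post-baseline unless otherwise indicated based on available start date/time combination". The other exception allowed is an eCRF entry showing that the event began before the first study medication. SAP 6.1 supplies the date: "Reference start date is defined as the day of the first dose of study intervention". Neither section singles out the injection.
- **SAP Appendix 2**, treatment-emergence algorithm, row for a known start date: "If start date >= study med start date, then TEAE". No clock time is used.
- **SAP Table F.** The TEAE baseline is Visits 1 to 3 and the post-baseline window opens at Visit 3.01. Visit 3 is not divided at dosing.

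Protocol 1.3 and 4.1.3 have both products given at Visit 3 as its last procedure: two injections and one tablet. In the rimegepant arm the tablet is active and the injections are placebo; in the galcanezumab arm it is the reverse. SAP 5.2 treats either product as exposure: the safety set is "all participants who are exposed to study intervention (either injection or ODT"). Protocol 6.4 says that the date and time of each dose will be recorded.

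**The concern.** Exposure starts with whichever product is given first, but 20.1 starts the clock only at the injection. A participant who has already taken the tablet can be classed as not yet dosed. The clock then follows the placebo in the rimegepant arm and the active product in the galcanezumab arm.

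Safety and tolerability are a stated secondary objective, TEAEs are the first measure listed under it, and adverse events are compared between arms by Fisher's exact test. A rule that can miss immediate reactions to one comparator's active product but not to the other's should not stand in a head-to-head trial, even if it rarely operates. The effect can also outlast the day. Under 20.1 the maximum baseline severity for a Lowest Level Term (LLT) is the bar that later events must exceed, so a reaction wrongly placed in baseline can hide recurrences of equal or lower severity.

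The conflict with Appendix 2 is a separate matter. Dosing comes last at Visit 3, so an event earlier that day, before any dose, is plausible, and the SAP gives two different statuses for it.

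**Working it through.** The plan gives no figure to reproduce. The check applies each stated rule to every ordering of tablet, injection and event on the Visit 3 date.

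**Inputs.** Let *A* be the event start time, *I* the first injection time and *T* the first tablet time. Clock times are in minutes and illustrative. The event is assumed to be new for its LLT, so that post-baseline means treatment-emergent.

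**Rules as written.**
- SAP 20.1: pre-dose if *A* < *I*; post-dose if *A* > *I*.
- SAP 6.2: pre-dose if *A* < min(*I*, *T*); otherwise post-baseline.
- Appendix 2, known start date: treatment-emergent whenever the event date is on or after the first-dose date.

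| Case | 20.1 | 6.2 | Appendix 2 |
|---|---|---|---|
| Before both (*T*=0, *I*=15, *A*=−10) | pre | pre | **TEAE** |
| Between, tablet first (*T*=0, *I*=15, *A*=10) | **pre** | post | TEAE |
| Between, injection first (*I*=0, *T*=15, *A*=10) | post | post | TEAE |
| After both (*T*=0, *I*=15, *A*=30) | post | post | TEAE |
| Event at injection time (*T*=0, *I*=15, *A*=15) | no time rule | post | TEAE |
| Tablet only, no injection (*T*=0, *A*=10) | no time rule | post | TEAE |

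**Reading the table.**
1. In the second row 20.1 gives a definite answer, pre-dose, after exposure has begun. The worst-case default does not rescue it, because the status was not indeterminate.
2. In the first row Appendix 2 is the outlier: it counts an event that preceded all dosing.
3. In the last two rows 20.1's time comparison gives no result, but its worst-case default does: treatment-emergent. For the tablet-only case this follows directly; for equal times it is a reasonable reading. These rows are not live conflicts.
4. With the injection first, 20.1 and 6.2 agree on every timed event.

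**By arm, second row.** A reaction to galcanezumab cannot start before the injection, so no such reaction is lost. A reaction to active rimegepant can start between tablet and injection, so it can be. A coincidental event in the same interval is classed as pre-dose in either arm.

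**Scale.** The minimum of about 575 randomized 1:1 gives 575 / 2 = 287.5 per arm. One reclassified participant is 100 / 287.5 = 0.35 percentage points. The documents give no event count and no tablet-to-injection interval. For an assumed 1 to 10 participants in one arm the shift would be 0.35 to 10 × 100 / 287.5 = 3.48 points. That range shows scale only; it is not an estimate.

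**The case against.** The strongest reply is that the tablet-first order is not the one described. Protocol 6.3 sets out injection training and administration first and then the tablet, and Protocol 4.1.3 lists the injections first. Both products close the visit, so the interval is probably short. This stands as a limit on size. It does not remove the conflict, because neither section makes the order a requirement.

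A second reply is that Appendix 2 is headed as a set of partial-date conventions and 20.1 refers to it only for partial dates, so the specific time rule in 20.1 governs Visit 3. That is a sensible reading, and the author may have intended it. But the row in question is for a known start date, and nothing in the SAP says which text prevails.

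A third reply is that the events are not lost from reporting. SAP 20.1 lists both TEAEs and non-TEAEs, a summary of all SAEs is planned (although Table F opens that window at Visit 3.01), and all events leading to study discontinuation are summarized. This is correct, and limits the harm to the TEAE tables and comparisons.

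Three stronger readings are tempting and not supported:
- **That the rule biases the comparison against one arm in general.** It is the same in both arms and also moves coincidental events after a placebo tablet. Only for drug-caused reactions is the effect confined to rimegepant, and only when the tablet comes first.
- **That one event can receive three different answers.** Status is binary, and no case above yields more than two outcomes.
- **That tablet-only participants or missing times fall through.** The worst-case default covers them. It would also catch a tablet reaction that led to no injection being given, since no injection time would then exist.

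**Conclusion.** The point holds in a limited form. There are two inconsistencies: 20.1 against 6.2 for an event between a first-given tablet and the injection, where 20.1 gives a definite but wrong pre-dose status; and Appendix 2 against both for an event on the Visit 3 date before any dose. The first depends on the tablet preceding the injection, on an event starting in that interval and on its clock time being recorded. The second does not depend on dosing order.

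The effect on overall TEAE percentages is probably small, at about 0.35 points of an arm per participant at minimum enrolment, with no count in the documents. It matters most for rare immediate reactions, where one case carries weight, and through the carry-over into baseline severity. The primary and key secondary efficacy analyses are untouched. It is worth correcting because programmers following different sections could produce different TEAE tables.

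**What to change.** State one rule in SAP 20.1, 6.2 and Appendix 2, and align Table F with it:

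- An event on the first dosing day is post-dose if it starts at or after the earlier of the first tablet time and the first injection time.
- It is pre-dose only if it starts before both.
- Where a needed time is missing, the worst-case default already in 20.1 continues to apply.

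In Appendix 2, the known-start-date row should send events dated on the first dosing day to this rule. In Table F, the TEAE baseline and post-baseline windows should divide Visit 3 at the first dose.

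The cost is a wording change and minor programming before unblinding. One check comes first. Protocol 6.4 says that dose times are recorded, but the eCRF dose items in SAP 15 are set out around the monthly injection schedule, so confirm that the Visit 3 tablet time is in the analysis database.
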